# **PASS** Information

Title	One Year Post-discharge Clinical and Economic Outcomes among
	Patients with ACS Managed with PCI and Treated with Prasugrel
	vs. Clopidogrel
Study Alias	H7T-MC-B022
Version identifier	1.0
Date of last version	
EU PASS Register No:	Not Applicable
Active substance	Prasugrel
Medicinal product(s):	Effient
Comparator product:	Clopidogrel
Product reference:	N/A
Procedure number:	N/A
Marketing authorisation holder(s)	Eli Lilly and Co.
Joint PASS	No
Research question and objectives	Primary objective: To compare major adverse cardiovascularevents (MACE) up to one year after hospital discharge among ACSpatients with no history of TIA or stroke, managed with PCI, andtreated with prasugrel vs. clopidogrel.Secondary objectives: To compare demographics, baseline clinicalcharacteristics, treatment patterns, and clinical and economicoutcomes up to one year after hospital discharge among ACSpatients with no history of TIA or stroke, managed with PCI, andtreated with prasugrel vs. clopidogrel.
Country of study	US
Author	OptumInsight ([name])/Lilly ([name])

Approval Date:

# 2. List of Abbreviations

Term	Definition
ACEi	Angiotensin converting-enzyme inhibitor
ACS	Acute Coronary Syndrome
ACS-PCI	ACS managed with percutaneous coronary intervention (PCI)
ADP	Adenosine diphosphate
ADP-ri	Adenosine diphosphate receptor inhibitor
AE	Adverse event
ANCOVA	Analysis of covariance
AR	Adverse reaction
ARB	Angiotensin II receptor blocker
ARC	Academic Research Consortium
BMS	Bare metal stent
CABG	Coronary artery bypass graft
СВС	Complete blood count
CCU	Coronary Care Unit, Cardiac Care Unit, or Critical Care Unit
CDM	Charge data master
CHF	Congestive Heart Failure
СКД	Chronic kidney disease
CLT	Central Limit Theorem
COPD	Chronic obstructive pulmonary disease
CRF	Case report form
СТ	Computed tomography
CV	Cardiovascular
CXR	Chest x-ray
DES	Drug eluting stent

DSI	Daiichi Sankyo Incorporated
ECG	Electrocardiogram
EMR	Electronic medical record
ERB	Ethical Review Board
FDA	Food and drug administration
FDAMA 114	FDA Modernization Act section 114
GLM	Generalized linear model
HIPAA	Health Insurance Portability and Accountability Act of 1996
ICD-9 CM	International Classification of Disease-9th Ed. Clinically Modified
ICU	Intensive care unit
IRB	Institutional review board
Lilly	Eli Lilly and Company
LOS	Length of stay
MACE	Major Adverse Cardiovascular Event(s)
MI	Myocardial infarction
MRI	Magnetic resonance imaging
NACE	Net Adverse Clinical Events
NCPDP	National Council for Prescription Drug Programs
NSTEMI	Non-ST-segment elevation myocardial infarction
OAP	Oral antiplatelet
OLS	Ordinary Least Squares
PCI	Percutaneous coronary intervention
PFT	Pulmonary function tests
РРІ	Proton pump inhibitors
PRBC	Packed red blood cells
RCT	Randomized clinical trial
RX	Prescription claims data asset

SAE	Serious adverse event
SAP	Statistical Analysis Plan
SAR	Serious adverse reaction
SD	Standard deviation
SSDI	Social security death index
STEMI	ST-segment elevation myocardial infarction
TBD	To be determined
TIA	Transient Ischemic Attack
TRITON-TIMI 38	Trial to Assess Improvement in Therapeutic Outcomes by Optimizing Platelet Inhibition With Prasugrel–Thrombolysis in Myocardial Infarction 38
UA	Unstable angina
WB	Whole blood

# 3. List of Definitions

#### Acute Coronary Syndrome (ACS)

A cluster of events with coronary artery disease complicated by an acute intracoronary thrombus including ST elevation myocardial infarction (STEMI), non-ST elevation myocardial infarction (NSTEMI), and unstable angina (UA).

#### ACS-PCI Hospitalization

An inpatient admission with primary or secondary diagnosis codes for ACS and procedure codes for a percutaneous coronary intervention (PCI).

#### Adherence

Adherence with the post-discharge index therapy will be estimated using the proportion of days covered (PDC) during two specified time intervals: 3 months and 12 months post-discharge index therapy initiation. PDC will be calculated by dividing the total days supply of filled medications during the 3- and 12-month intervals by 90 and 365 days, respectively. For purposes of this study, the days supply of overlapping fills will be pushed out to start the day after the end of the previous fill's supply. The calculation will be corrected for inpatient admissions, under the assumption that during a hospitalization medication was supplied by the facility. PDC  $\geq 80\%$  will be considered adherent.

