### 8.2. Secondary Objectives

- 2. To compare demographics and baseline characteristics between patients treated with prasugrel versus clopidogrel before propensity adjustment.
- 3. To compare index therapy treatment patterns with prasugrel versus clopidogrel including adherence, discontinuation, persistence, and switching as listed in Table 1 through 1) three months and 2) one year post-discharge from the index hospitalization.
- 4. To compare NACE and its components with prasugrel versus clopidogrel including bleeding as listed in Table 1 through 1) 30 days, 2) three months, and 3) one year post-discharge from the index hospitalization.
- 5. To compare all-cause health care resource utilization (including length of stay of the index hospitalization and subsequent readmissions) and costs with prasugrel versus clopidogrel through 1) 30 days, 2) three months, and 3) one year post-discharge from the index hospitalization. Resource utilization and costs will be stratified as listed in Table 1.
- 6. To compare disease-related (including MI, revascularization, stroke, unstable and stable angina, congestive heart failure, and bleeding as listed in Table 1) health care resource utilization and costs with prasugrel versus clopidogrel through 1) 30 days, 2) three months, and 3) one year post-discharge from the index hospitalization.
- 7. If differences in treatment patterns (i.e, adherence, persistence, switching, and discontinuation) are found, then assess factors associated with adherence, persistence, switching, and discontinuation of a) prasugrel and b) clopidogrel patients through one year post-discharge from the index hospitalization.
- 8. If differences in treatment patterns are found, then examine associations between treatment patterns (adherence, persistence, switching, and discontinuation) and outcomes (clinical: all-cause mortality, MACE, inpatient readmissions; economic: total costs) for a) prasugrel and b) clopidogrel patient through one year post-discharge from the index hospitalization.

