## 9.1.2. Claims Database Sample

### 9.1.2.1. Inclusion Criteria

The primary and secondary objectives for the study will be addressed with commercial and Medicare Advantage health plan enrollees who meet all of the following inclusion criteria and none of the exclusion criteria below:

- ACS-PCI Hospitalization: At least one inpatient (IP) hospitalization with primary or secondary ACS diagnosis codes *and* PCI or coronary stent procedure codes between 01 September 2009 and 31 May 2013 (selection window). Note:
  - The *index admission date* will be defined as the admission date of the first such ACS-PCI hospitalization.
  - Both the index admission and discharge dates must occur during the selection window.
  - The *study index date* will be defined as the discharge date of the first such ACS-PCI hospitalization.
- **ADP-ri Index Fill**: At least one outpatient pharmacy fill for prasugrel or clopidogrel between the study index date and 30 days post-discharge from the index hospitalization. Note:
  - The *index therapy fill date* will be defined as the date of the first such fill.
  - The ADP-ri filled on the index therapy fill date will be defined as the *post- discharge index therapy*.
- Age: Aged  $\geq 18$  years as of the study index date.

<sup>13 Effient [package insert]. Indianapolis, IN: Eli Lilly and Company; 2013.

<sup>14 Prasugrel was approved by the FDA in July 2009.

• **Continuous Enrollment**: Continuously enrolled in a commercial or Medicare Advantage health plan with medical and pharmacy benefits for 12 months before the index admission date (baseline) and for at least 3 months after the index hospitalization discharge date (i.e., the study index date) or until death, if sooner (follow-up).

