### 9.1.4. Study Timeframe

Five observation periods will be defined:

- 1. **Index hospitalization period**: Days between, and including, the admission and discharge dates of the index hospitalization.
- 2. **Baseline period**: 12 months before the index hospitalization admission date.
- 3. **ADP-ri index selection period**: Study index date to 30 days post-discharge from the index hospitalization.
- 4. **Variable follow-up period**: Days on and after the study index date until 3 or more months after the study index date or until death, if sooner. Maximum follow-up will be 12 months.
- 5. **Fixed follow-up period**: Days on and after the study index date until 12 months after the study index period or until death, if sooner. This one year follow-up period will be used to assess the primary endpoint as a secondary objective, adherence, persistence, and costs.

Figure 1 illustrates the study timeframe.

Figure 1. Study Timeframe

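### The 12-month PDC keeps a 365-day denominator for patients who die, so early death produces the non-adherent label that Objective 8 then relates to mortality

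*Protocol*

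**What the plan says.** Protocol section 3 (List of Definitions), Adherence, measures adherence over two intervals, "3 months and 12 months post-discharge index therapy initiation". The formula is explicit: "PDC will be calculated by dividing the total days supply of filled medications during the 3- and 12-month intervals by 90 and 365 days". Two adjustments follow. For overlaps, "the days supply of overlapping fills will be pushed out to start the day after the end of the previous fill's supply". For hospital stays, "The calculation will be corrected for inpatient admissions", on the assumption that the facility supplied the drug. A patient with PDC of at least 80% "will be considered adherent". No adjustment for death is given.

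Section 9.1.2.1 asks for three months of enrolment after discharge or enrolment up to an earlier death, so patients who die early are kept. Section 9.1.4 ends the fixed follow-up period at 12 months or death and says of it: "This one year follow-up period will be used to assess the primary endpoint as a secondary objective, adherence, persistence, and costs".

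Section 8.2, Objective 8, applies only if treatment patterns differ. It would "examine associations between treatment patterns (adherence, persistence, switching, and discontinuation) and outcomes", naming all-cause mortality, MACE, readmissions and total costs, within each drug cohort and over the year after discharge.

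**The concern.** Follow-up for adherence stops at death, but the divisor stays at 365. A patient who took the drug without a gap until dying in month six is scored as if six further months of supply had been missed. If that score is then set against mortality in the same year, part of the association is arithmetic: dying early creates the label. A reader of Objective 8 could take this for evidence that poor adherence kills.

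There is a smaller, separate question about the numerator. As worded, it is a sum of supply dispensed, and nothing cuts supply that runs past the interval end.

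**Working it through.** The protocol gives no computed PDC figure to reproduce, so the check is direct arithmetic on its formula.

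**Inputs.** From the protocol: divisors 90 and 365, cut-off 80%, time counted from first fill. Assumed, because the protocol is silent: fills of 30 or 90 days, refilled on time or about 10-25% early; deaths uniform over the year; 50-70% of survivors adherent; the same underlying adherence in those who die and those who do not.

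**Step 1, when a perfect user can reach 80%.** The cut-off needs 0.80 × 365 = 292 days of supply.
- On-time 30-day fills: nine give 270/365 = 74.0%, ten give 300/365 = 82.2%, and the tenth falls on day 9 × 30 = 270.
- On-time 90-day fills: three give 270/365 = 74.0%, and the fourth falls on day 3 × 90 = 270.
- About 10% early (every 27 or 81 days): limit about day 244. About 20% early (every 24 or 72 days): about day 217. 90-day fills every 68 days: about day 205.
- If supply is instead cut at death: day 292.

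With on-time 30-day fills, a perfect user who dies on day 60, 90, 180 or 270 scores 16.4%, 24.7%, 49.3% or 74.0%. Divided by days alive, each would score 100%. With uniform deaths, 270/365 = 74% of deaths fall by day 270.

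For the 3-month PDC the limit is about day 60 with on-time 30-day fills. There is none with a 90-day first fill, since 90/90 = 100% at once.

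**Step 2, the association created when adherence has no effect.** Let D be the limit from step 1, a the adherent share of survivors, and q = 1 − D/365. Among those who die, P(adherent) = q × a. The false relative risk, non-adherent against adherent and treating deaths as rare, is

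[(1 − qa)/(1 − a)] / [qa/a] = (1 − qa) / [(1 − a)q].

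| D | q | a = 0.5 | a = 0.6 | a = 0.7 |
|---|---|---|---|---|
| 270 | 0.260 | 6.7 | 8.1 | 10.5 |
| 244 | 0.332 | 5.0 | 6.0 | 7.7 |
| 205 | 0.438 | 3.6 | 4.2 | 5.3 |

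**Step 3, numerator.** Moving overlapping fills forward changes their start dates but not the sum of days supply.
- 3 months: a 30-day fill on day 0 and a 90-day fill on day 60 give (30 + 90)/90 = 133%. Days 0-29 and 60-89 are covered, which is 60/90 = 67%.
- 12 months: seven on-time 30-day fills and a 90-day fill on day 360 give 300/365 = 82%, against (210 + 5)/365 = 59% covered.

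Both examples cross the 80% cut-off.

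**Step 4, whether anything else repairs it.** The sensitivity analysis with 70% and 90% cut-offs (section 9.6.6) only moves the limit. With on-time 30-day fills, 70% needs 255.5 days, reached by the ninth fill on day 240; 90% needs 328.5 days, reached by the eleventh on day 300. Time-varying exposure appears in section 9.6.5.2 under the primary MACE model, as an option, and not for Objective 8.

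**The case against.** The strongest reply is that the measure is called proportion of days covered, and that dating each fill's supply makes little sense if fills are merely added up, so days covered were probably intended. That is fair for the numerator and makes it the smaller flaw. With non-overlapping 30-day fills, the overhang on the 12-month measure is at most 29/365 = 8%. It does not help the denominator: under that reading, with supply also cut at death, the limit moves later, to day 292.

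A second reply is that Objective 8 is secondary and conditional, that its method is not set out, and that section 9.6.5.2 leaves model details to the SAP. This stands in part: the absence of a landmark from the protocol is no error in itself, and the relative risks above presume a crude comparison that the protocol does not prescribe. But the divisor of 365 is a stated rule, and it feeds whatever model is chosen.

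Several stronger readings are tempting and are not supported:
- That anyone dying before day 270 is non-adherent. The limit applies to the 12-month PDC, runs from the first fill, and depends on fill size and refill timing.
- That every outcome in Objective 8 shortens the exposure. Non-fatal MACE and readmission do not shorten the supply window, and hospital days are corrected for. There the issue is only that exposure and outcome share the same period.
- That discontinuation carries the same artefact. If its study-period end is taken as death, a patient who dies on drug is not a discontinuer, and early death leaves less time to stop.
- That the cohort comparison in Objective 3 is biased by fill size. This is possible, but the protocol does not say that fill sizes differ between prasugrel and clopidogrel.

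**Conclusion.** The concern holds for the 12-month PDC against all-cause death and the death component of MACE. A perfect user on 30- or 90-day fills who dies by about day 270 after first fill (about day 205-244 with early refills) is labelled non-adherent by the formula alone. In a crude comparison the resulting false mortality relative risk is about 3.6-10.5. That range rests on uniform deaths, 50-70% of survivors adherent, the assumed refill timing and rare deaths; it shows the size of the artefact and does not predict the study's result. The missing cut at the interval end is a real but lesser defect.

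The effect is confined to secondary Objectives 3, 7 and 8, of which 7 and 8 are conditional. A reader might infer that the primary result is at risk. It is not, because the primary MACE analysis does not use PDC. The definition should be fixed before analysis, but it is not critical to the main conclusion.

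**What to change.** Redefine PDC. The numerator is the number of days in the interval with drug on hand, each day counted once, with supply cut at the interval end or at death. The denominator is days from first fill to the earliest of death, disenrolment or day 90/365. Keep the inpatient correction and say whether it acts on the numerator, the denominator or both. A patient who fills on time until death then scores 100% whatever the day of death.

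For Objective 8, classify patients by 3-month PDC among those alive, enrolled and event-free at day 90 after the first fill, and count outcomes only after that point. Alternatively, use time-varying adherence based on past fills only. The landmark must run from the first fill and not from discharge. The first fill may come up to 30 days after discharge, so a 90-day PDC window can extend to day 120 after discharge; a landmark at day 90 after discharge would use later information. Table 1 describes the adherence intervals as starting at discharge, so the two descriptions should be aligned.

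The data are retrospective claims, so the cost is protocol and SAP wording and some reprogramming. The drawback is that a landmark loses events in roughly the first three months and narrows the one-year scope of Objective 8; the time-varying version avoids this but takes more programming.

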### Adenosine diphosphate receptor inhibitor (ADP-ri)

ADP-ri medications are the oral antiplatelet agents: clopidogrel, prasugrel, ticagrelor, and ticlopidine.

### All-cause Mortality

Death specified as discharge status on an inpatient facility claim or by a date of death in the Social Security Death Index.

### Baseline

12 months before the index hospitalization admission date.

### Bleeding

Bleeding will be identified by ICD-9 diagnosis and/or procedure codes for bleeds and/or blood transfusions during medical encounters. Major/severe bleeding events will be defined by the presence of: 1) ICD-9 diagnosis and/or procedure codes for bleeding and  $\geq$ 3 units of blood transfused (per CPT or ICD-9 procedure codes) within an inpatient hospitalization, or 2)  $\geq$ 4 units of blood transfused (per CPT or ICD-9 procedure codes) with or without ICD-9 diagnosis and/or procedure codes) with or without ICD-9 diagnosis and/or procedure codes for bleeding, epistaxis, etc.), or 3) ICD-9

diagnosis codes for intracranial hemorrhage, or 4) ICD-9 diagnosis and/or procedure codes for blood transfusions followed by death for any reason within an inpatient hospitalization.

#### Cardiovascular (CV) events

Medical events related to clotting or emboli within the cardiovascular system.

#### Concomitant medications

Medications that have an overlapping days supply with the post-discharge index therapy (prasugrel or clopidogrel).

#### Discontinuation

Discontinuation of the post-discharge index therapy will be defined by a gap of 30 days or more in fills for the index therapy. The date of discontinuation will be defined by the run-out of days supply of the last prescription filled prior to the first 30-day gap in treatment, if any. The days supply of overlapping fills will be pushed out to start the day after the end of the previous fill's supply.

Discontinued therapy if:

- (End of study period) (run-out date of last fill)  $\ge$  30 days OR
- (start date of fillx+1) (run-out date of fillx 1)  $\ge$  30 days

The total number of fills for the post-discharge index therapy prior to discontinuation will also be calculated.

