### Follow-up

At least 3 months and no more than 12 months after the index hospitalization discharge date or until death, if sooner.

Health Care Resource Utilization

Medical Encounters

Medical encounters will be classified into the following categories of health care services:

- Inpatient admissions will be defined as hospitalizations during the study period

<sup>1 Berenson K, Casciano R, Makenbaeva D, Mozaffari E, Lamerato L, Corbelli J. Economic consequences of severe bleeding in patients with acute coronary syndrome in the USA. *Adv Ther*. 2010;27(8):564-579.

<sup>2 The run-out date will be defined as the pharmacy claim date + days supply.

- *Emergency department visits* will be defined as visits to emergency treatment centers or hospital emergency rooms during the study period
- *Ambulatory visits* will be defined as the following encounters during the study period:
  - office visits to primary or specialty care providers, urgent care clinics
  - outpatient hospitals visits
  - other ancillary settings including laboratory, radiology, and physical therapy
- *Pharmacy fills* will be defined as outpatient filled prescriptions (including initial fills and refills) during the study period

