#### Major Adverse Cardiovascular Event(s) (MACE)

MACE is a composite endpoint of CV events that has been widely used in the CV literature to characterize the overall efficacy or effectiveness of treatment. In this study, MACE will be defined as a composite measure based on the presence of any evidence for all-cause mortality, hospitalization for stroke, rehospitalization for myocardial infarction or unstable angina, or post-discharge revascularization (PCI or CABG).

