#### Switching

Switching will be defined by presence of a prescription for an alternative ADP-ri, not the postdischarge index therapy.

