### 9.6.5.2. Analysis of Continuous Outcomes

### Primary objective: One year MACE

In addition to KM curves, multivariate Cox proportional hazards models will be used to assess the primary objective using an *on treatment* approach where patients will be censored at the end of treatment exposure time window (time of discontinuation or switching) and not allowed to switch treatment groups on the basis of their treatment use. If high rates of switching and/or discontinuation (threshold will be specified in the SAP) are observed, then an *as treated* analysis, where patients will be censored at the end of treatment exposure time window but allowed to switch treatment groups on the basis of their treatment use, may be conducted as a secondary analysis. Time-varying treatment exposure and treatment status as a time-dependent covariate may be incorporated into the Cox proportional regression model(s) as appropriate. In addition, an approach where patients will be assigned to the treatment they are first exposed (based on first prescription fill post index hospitalization discharge), regardless of discontinuation or switching, will be used to assess the primary endpoint (up to one year MACE) as a secondary objective.

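### Primary on-treatment censoring is back-dated to supply run-out, so whether a non-fatal MACE in the refill gap counts depends on refilling after the event

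*Protocol*

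**What the plan says.** The trigger is in the list of definitions in Section 3 of the protocol, as follows: "Discontinuation of the post-discharge index therapy will be defined by a gap of 30 days or more in fills for the index therapy". But the assigned date is earlier than the trigger: "The date of discontinuation will be defined by the run-out of days supply of the last prescription filled prior to the first 30-day gap". Footnote 2 in the same section adds no grace period: "The run-out date will be defined as the pharmacy claim date + days supply".

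Section 9.6.5.2 applies this to the primary objective. In the on-treatment Cox model, "patients will be censored at the end of treatment exposure time window (time of discontinuation or switching"). The endpoint is a composite of "all-cause mortality, hospitalization for stroke, rehospitalization for myocardial infarction or unstable angina, or post-discharge revascularization (PCI or CABG"), so most of its components can be survived and can be followed by a change in prescribing.

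Three related provisions matter:
- Switching has its own definition in Section 3: "Switching will be defined by presence of a prescription for an alternative ADP-ri". Section 9.8 adds that switches are counted as discontinuations.
- Adherence (PDC) credits hospital days: "The calculation will be corrected for inpatient admissions, under the assumption that during a hospitalization medication was supplied by the facility". The discontinuation definition states no such credit.
- Section 9.6.5.2 also commits to a secondary analysis of MACE by first drug filled, ignoring discontinuation and switching. Section 9.6.6 lists a 60-day gap, item (c), among sensitivity analyses that may be done.

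**The concern.** A valid censoring rule lets a patient's status on a given day be decided from what is known by that day. Here, status on each of the 29 days after run-out stays open until it is known whether the patient refills. If a MACE occurs in that window, the deciding information comes after it, and a MACE is the kind of event that can change whether the same drug is filled again. Inclusion of the event can thus depend on its own consequences.

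The event admission may also lengthen the gap. The protocol assumes for PDC that the hospital supplies the drug, but it does not carry that assumption into the gap count.

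At stake is the primary hazard ratio. If patients on one drug refill it after an event less often than patients on the other, more of that cohort's gap events are dropped, and the comparison shifts for a reason unrelated to drug effect.

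**Working it through.** **The rule traced on one patient.** Supply runs out on day 0. A non-fatal MI occurs on day 10.
- Index drug refilled on day 25: the gap is 25 days, there is no discontinuation, the patient is on treatment on day 10, and the MI counts.
- No refill by day 30 and no other drug filled: the patient has discontinued, dated to day 0. Censoring falls on day 0 and the MI is dropped.
- Another ADP receptor inhibitor filled on day 15, index drug not refilled: if the switch date governs, censoring is on day 15 and the MI counts. If run-out governs, it is dropped. The text does not say which.
- Death on day 10 instead of MI: if the study period in the discontinuation formula ends at death, as follow-up does in Section 3, only 10 days have passed since run-out and the death counts. If it ends on a fixed date at least 30 days after run-out, the death is dropped. The term is not defined.

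The first two histories are identical up to day 10 and differ only in what follows.

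**The planning figure, for scale.** Section 9.4 states 92% power for HR 0.85, 12% one-year MACE on clopidogrel, a 3:1 ratio and two-sided 0.05. With 5,101 prasugrel patients, 3:1 gives 15,303 on clopidogrel.
- Prasugrel risk = 1 − 0.88^0.85 = 10.3%.
- Events ≈ 5,101 × 0.103 + 15,303 × 0.12 ≈ 2,362.
- Schoenfeld: √(2,362 × 0.25 × 0.75) × |ln 0.85| − 1.96 ≈ 1.46, so power is 92.8%.

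The stated figure reproduces. The censoring rule is a question of bias, and this figure is not in dispute.

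**Effect on the hazard ratio.** Let f be the share of MACE falling in gaps under 30 days. In each cohort, let r be the probability of an index refill within the gap given an event, divided by the same probability without an event. Then

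multiplier on HR = [(1 − f) + f·r(prasugrel)] / [(1 − f) + f·r(clopidogrel)].

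The protocol gives neither f nor r, so all values are assumptions. With r equal in both cohorts the multiplier is 1.00. With r = 0.9 in one cohort and 0.5 in the other:

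| f | Lower r on clopidogrel | Lower r on prasugrel |
|---|---|---|
| 5% | 0.995/0.975 = 1.020 | 0.980 |
| 10% | 0.990/0.950 = 1.042 | 0.960 |
| 15% | 0.985/0.925 = 1.065 | 0.939 |

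At the extremes a true 0.85 would be estimated at about 0.85 × 1.065 = 0.905 or 0.85 × 0.939 = 0.798.

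**Simulation with no drug effect.** Assumptions: 200,000 patients per arm; 30-day fills; hazard −ln(0.88)/365 per day in both arms; a gap at 25% of run-outs unless stated; 80% of gaps closed within 29 days when no event occurs. The standard error of each rate ratio is about 0.01.

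| Index refill after an event, prasugrel / clopidogrel | Protocol rule | Run-out + 30 days |
|---|---|---|
| 0.8 / 0.8 | 1.01 | 1.01 |
| 0.7 / 0.4 | 1.03 | 0.99 |
| 0.4 / 0.7 | 0.97 | 1.00 |
| 0.7 / 0.4, gaps at 20% / 35% of run-outs | 1.06 | 1.00 |

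The fixed tail stays at 1 within simulation error; the protocol rule moves with the assumed refill difference.

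**The case against.** The protocol limits the damage itself. It commits to a first-exposure analysis of the same endpoint, which this problem cannot touch. That stands, but the analysis is secondary and does not repair the primary one. The optional 60-day gap does not help, because it lengthens the period of later behaviour that decides inclusion.

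A reader might infer more than the text supports:
- **That every event followed by a switch is erased.** Section 9.6.5.2 names switching as a censoring time of its own, so such an event may well count. The documents leave the governing date open.
- **That fatal and non-fatal events are necessarily treated differently.** This holds on only one reading of the undefined end of the study period.
- **That the bias cannot cancel because the two drugs are switched unequally after events.** Nothing in the protocol shows this.
- **That all MACE expected just after run-out measure the bias.** If 30%, 40% or 60% of 20,404 patients run out without refilling, 20,404 × share × 29/365 × 0.128 gives about 62, 83 or 124 events. Most of those patients would not have refilled anyway, and leaving out their events is what censoring at run-out intends. The count does not measure a shift in the hazard ratio.

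It is also fair to say that crediting inpatient days is a detail that an analysis plan often settles. The back-dated date is different: the protocol itself fixes it.

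**Conclusion.** The defect stands for non-fatal MACE on days 1 to 29 after run-out in patients who do not switch: inclusion in the primary analysis turns on refilling after the event. For switchers and for deaths in the gap, the text is ambiguous and has to be settled. Events on covered days are unaffected.

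The hazard ratio is close to unbiased if post-event refilling is the same in both cohorts. If it differs, the assumed inputs (f of 5% to 15%, r of 0.5 to 0.9) give a shift of up to about 6% in either direction, against a planned 15% reduction. Neither size nor direction can be determined from the protocol. The rule should be changed before outcomes are analysed.

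**What to change.** In the censoring rule for the primary analysis:
- Censor at run-out plus a fixed 30 days, or at the first fill of another ADP receptor inhibitor if that comes earlier.
- Count every MACE, including deaths, up to that date. This settles both the switch date and deaths in the gap.
- Extend supply by inpatient days, as already done for PDC.
- Keep censoring at run-out as a sensitivity analysis, and pair the 60-day gap in sensitivity analysis (c) with a 60-day tail.

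The main change is about one sentence. The cost is that up to 30 days of possibly untreated time per discontinuer is counted as exposed, under the same rule in both cohorts. The run-out sensitivity analysis shows how much that matters.
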